4.5.1 Major Protocol Deviations Leading to Exclusion from the PPS Analysis

A protocol deviation (PD) is any change, divergence, or departure from the study design or procedures of a study protocol. A protocol deviation may be a reason to remove data from an analysis set at the time of analysis. PDs can be either observable or programmable. Programmable PDs are those PDs that can be programmed from the data recorded in the clinical database. Observable PDs are PDs identified by Clinical Research Associates (CRAs) or other team members.

PDs will be classified as major and minor using a prespecified list of types of deviations. Major PDs are defined in accordance with ICH E3 as important PDs related to study inclusion or exclusion criteria, conduct of the trial, subject management or subject assessment resulting in the potential to jeopardize the safety or rights of the trial subjects or the scientific value of the trial.

All PDs will be evaluated before unblinding and most will be classified into the following categories:

- Subject randomized and did not satisfy entry criteria
- Subject developed withdrawal criteria during the study but was not withdrawn.
- Subject received the wrong treatment or incorrect dose
- Subject took an excluded concomitant medication
- Key study procedures missed or performed out of window

The impact of major PDs on the efficacy, immunogenicity and/or safety results will be investigated by assessing the robustness of the study results.

Major PDs will lead to exclusion of the subject or part of the subject's data from at least one analysis set.

The number of subjects in any and by PD category will be summarized by treatment group, center and overall. Individual subject listings will be provided in an appendix, sorted by subject and by PD category.

Prior to unblinding the analysis, designated Seqirus staff will develop a memo that describes the PDs that led to exclusions from analysis sets. This Exclusion Memo will be signed off by at least the Biostatistician and the Clinical Scientist and will be included in the trial master file.

Prematurely terminating study participation for reasons such as withdrawal of consent or occurrence of AEs (including death) is not considered as a PD. Any missing assessments that should have otherwise been collected for that subject later in the study is also not considered as a PD.

Statistical Analysis Plan – Final v2.0

Sponsor Name: Seqirus UK Limited
Sponsor Protocol ID: V130_14

Deviations from the protocol will be documented on an ongoing basis by the study monitors and lead CRA or designee throughout the study period.

At the time of database lock, prior to unblinding and while the major PDs are being reviewed, the project manager or designee will forward all relevant documentation highlighting PDs to the study statistician. These deviations will be included in the protocol deviation document for agreement and will be listed with the PDs in the clinical study report (CSR).

PD listings will be reviewed by Seqirus prior to the finalization of the population datasets, which will occur prior to unblinding. The list will be used to determine which subjects should be excluded from either the FAS or the PPS.

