### 3.3.1 Subjects 6 through 11 months old at enrollment

To maintain the blind in the study, all subjects aged 6 through 11 months at enrollment will receive a MenC vaccine at visit 5. According to the MenC (*Neisvac-C*) vaccine prescribing information subjects that received their first dose < 12 months of age should receive a second dose, at least 6 months after the first dose, to complete their primary immunization. For subjects aged  $\geq 12$  months at first vaccination, only one dose of the MenC vaccine is necessary. To meet these requirements and to maintain the blind in the study, all subjects aged 6 through 11 months at enrollment will receive a dose of the MenC vaccine at visit 5.

Except in the case of medical necessity, a subject's treatment should not be unblinded without the approval of the Sponsor. In such instance, every effort should be made to contact the Sponsor prior to unblinding. If unblinding occurs, by either accidental unblinding or emergency unblinding for a serious adverse event, prior to completion of the study, the investigator must promptly contact the Sponsor and document the circumstances in IRT. In case of an emergency, the information can be retrieved by the Investigator from the IRT system either via web or phone (a 24/7 backup service). If the subject or blinded site staff is unblinded by the Investigator, the subject could be removed from an Analysis Set.

Investigators, Seqirus study team, all laboratory personnel involved in processing samples and performing laboratory assays and others who are directly involved in the conduct of the trial or in the analysis of the final trial results, or have contact with study centers, will remain blinded to the treatment codes and interim analysis results until the database has been locked for final analysis.

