### **8.3.8 Protocol Deviations**

A protocol deviation is any change, divergence, or departure from the study design or procedures of a study protocol. A protocol deviation may be a reason to remove data from an analysis set at the time of analysis. CSR-reportable (major) protocol deviations will be defined as exclusionary from the analysis according to protocol objectives and endpoints, which will be specified in the Protocol Deviation Specifications to this study protocol. In some cases, exclusion of data may be due to a reason other than a protocol deviation, e.g. early termination.

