4.4 Full Analysis Set (FAS), Efficacy/ Immunogenicity Set

FAS, Efficacy

All subjects in the All Enrolled Set who are randomized, who received at least one dose of study vaccination and are evaluated for efficacy at more than 14 days after the last vaccination.

FAS, Immunogenicity

All subjects in the All Enrolled Set who are randomized, who received at least one study vaccination and provide evaluable serum samples at both baseline (Day 1) and 28 days after last vaccination (Day29/57).

Last vaccination is at Visit 1 for "previously vaccinated" subjects and at Visit 2 for "not previously vaccinated" subjects.

Statistical Analysis Plan – Final v2.0

Sponsor Name: Seqirus UK Limited
Sponsor Protocol ID: V130_14

In case of vaccination error, subjects in the FAS sets will be analyzed "as randomized" (i.e., according to the study vaccine a subject was designated to receive, which may be different from the study vaccine the subject actually received).

If a subject is unblinded during the study, he/she will be included in the FAS.

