6.5 Efficacy

6.5.1 Primary Efficacy Endpoints Analysis

The primary efficacy analysis will be based on the FAS Efficacy. Eligible subjects for FAS analysis are subjects who are randomized and received at least one study vaccine and will be analyzed according to their randomized study vaccine (intent-to-treat analysis). Absolute vaccine efficacy will only be assessed for RT-PCR confirmed influenza episodes (primary efficacy endpoint 1a) and culture confirmed antigenically matched influenza episodes (primary efficacy endpoint 1b) with first onset of illness occurring at > 14 days after the last vaccination was administered in the treatment period until the end of the influenza season. Additionally, the primary objective will be evaluated in PPS Efficacy.

Time-to-event methodology based on a proportional hazard model will be used for all efficacy analyses to estimate the hazard ratio (HR). Absolute vaccine efficacy (aVE) against first occurrence RT-PCR confirmed influenza cases will be determined using a standard formula: $aVE = 1 - HR$ where HR is the hazard ratio for RT-PCR influenza confirmed cases in the QIVc group versus the comparator group. The HR will be estimated by a proportional hazards regression model, described below. For which the following null (H0) and alternative (H1) hypotheses will be tested:

$$H_0: 1 - HR \leq 0 \text{ versus } H_1: 1 - HR > 0$$

where HR is a hazard ratio of QIVc versus comparator and VE is vaccine efficacy. For both primary efficacy objectives, the HR and the related 97.5% CI of HR, for onset of first RT-PCR confirmed influenza will be estimated by a proportional hazards regression model with treatment effect as a fixed effect and stratifying covariates as random effect:

$$h_i(t|X) = h_0(t) \exp(\beta^T X + b^T Z),$$

with t denoting time to the influenza, β is the effect of treatment group indicated by X , b is random effect (assumed as a multivariable random gaussian variable with zero mean and diagonal covariance matrix), Z is random effect covariate (reflecting randomization strata).

Subjects that did not experience an event during observation period (be > 14 days after last vaccination up to end of influenza season) and subjects that dropped out from the study during observational period will be censored (right censoring) at the last available date in the eCRF prior to the end of influenza season.

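### SAP 4.5.1 lets the protocol-deviation list remove subjects from the FAS, although the FAS Efficacy definition has no deviation criterion

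*SAP*

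**What the plan says.** SAP 4.5.1 is headed "Major Protocol Deviations Leading to Exclusion from the PPS Analysis". It describes how deviations are classified, reviewed and documented, and it contains two rules on exclusion. The first is general: "Major PDs will lead to exclusion of the subject or part of the subject's data from at least one analysis set". The second closes the section and concerns the deviation listings that the sponsor reviews before the population datasets are finalised: "The list will be used to determine which subjects should be excluded from either the FAS or the PPS".

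SAP 4.4 defines FAS Efficacy as "All subjects in the All Enrolled Set who are randomized, who received at least one dose of study vaccination and are evaluated for efficacy" more than 14 days after the last vaccination. Protocol 8.3.4 asks for randomisation, a study vaccination and efficacy data. Neither definition mentions deviations. SAP 6.5.1 makes this the primary set, describes its members as randomised subjects who had at least one study vaccine, and says they "will be analyzed according to their randomized study vaccine (intent-to-treat analysis"). Protocol 8.4.2.2.1 agrees.

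Two protocol passages are more general. Section 8.3.8 says "CSR-reportable (major) protocol deviations will be defined as exclusionary from the analysis according to protocol objectives and endpoints", without naming a set. Section 3.3.1 says that after unblinding by the investigator "the subject could be removed from an Analysis Set", and SAP 2.2 repeats this.

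**The concern.** The closing sentence of SAP 4.5.1 makes the deviation list a basis for leaving the FAS. The definition of the FAS gives no such basis, and the intent-to-treat label implies there is none. Protocol 3.8 refers to the SAP for deviations and their consequences, so this sentence is operative text.

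Most of the deviation categories in SAP 4.5.1 (wrong treatment or dose, excluded medication, procedures missed or out of window, withdrawal criteria not acted on) arise after randomisation. If such events are related to treatment or to outcome, removing subjects because of them weakens the comparison that randomisation protects. The plan gives no rule for which deviation would have this consequence in the FAS, so membership of the primary set would partly rest on judgement.

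**Working it through.** **The passages side by side**

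| Situation | FAS Efficacy | PPS | Source |
|---|---|---|---|
| Wrong vaccine given | Kept, analysed as randomised | Excluded | SAP 4.4, 4.5 |
| Unblinded (a major deviation, with an exception for pharmacovigilance unblinding for a SUSAR) | Kept | Excluded | SAP 2.2, 4.4, 4.5 |
| Dose not at the scheduled time | Not a criterion | Criterion | SAP 4.4, 4.5; Protocol 8.3.4, 8.3.5 |
| Non-study influenza vaccine or prohibited treatment | Not mentioned | May be excluded | Protocol 6.4 |
| Any listed deviation | May be excluded | May be excluded | SAP 4.5.1, closing sentence |

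The last row does not fit the others. No passage names a deviation that takes a subject out of FAS Efficacy.

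**The plan's own figures first**

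Inputs (SAP 2.3 and 6.8): 1:1 allocation, one-sided alpha 0.0125, power 90%, HR 0.60 for 1a and 0.50 for 1b. The Schoenfeld formula is D = 4(z₀.₉₈₇₅ + z₀.₉₀)² / (ln HR)².

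- 1a: 4(2.2414 + 1.2816)² / (ln 0.60)² = 190.25, so 191 cases, as stated.
- 1b: 4(2.2414 + 1.2816)² / (ln 0.50)² = 103.33, so 104 cases, as stated.

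Power at D cases is Φ(|ln HR|·√D/2 − 2.2414). It is 90.1% at 191 (1a) and 90.2% at 104 (1b).

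**Illustration 1: loss of cases**

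The share lost is an assumption. The loss is taken as equal in both arms and not replaced, starting from exactly the minimum number of cases.

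| Cases lost | 1a cases | 1a power | 1b cases | 1b power |
|---|---|---|---|---|
| 1% | 189 | 89.8% | 103 | 89.9% |
| 5% | 181 | 88.4% | 99 | 88.6% |
| 10% | 172 | 86.6% | 94 | 86.8% |

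**Illustration 2: a result near the boundary**

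This uses a case-count approximation with equal follow-up and no interim look. For a QIVc cases and b comparator cases, the 97.5% lower limit for VE is 1 − exp[ln(a/b) + 2.2414·√(1/a + 1/b)]. With 191 cases the critical HR is exp(−2×2.2414/√191) = 0.723, a VE of 27.7%.

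- 80 v 111: lower limit −0.1%. Remove two QIVc cases (78 v 111): +2.1%.
- 79 v 112: lower limit +2.0%. Remove four comparator cases (79 v 108): −1.9%.

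These splits are chosen to sit at the boundary. They show sensitivity and do not predict anything.

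**The case against.** The best defence is that the list only helps to apply SAP 4.4. FAS Efficacy needs vaccination and evaluation after day 14. FAS Immunogenicity needs evaluable serum at both time points, so a missed procedure can decide membership by definition. SAP 4.5 and 6.2 both expect some FAS exclusions. This reading is possible, but the sentence does not limit itself to it: it ties exclusion to the deviation listing and not to the 4.4 criteria.

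The second defence is procedural. Major and minor deviations follow a prespecified list, all are evaluated before unblinding, and a signed memo records the exclusions. This guards against selection made with knowledge of the arm. It does not restore comparability if deviations are related to treatment or outcome, and it does not say who may leave the FAS.

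Three objections stand in full:

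- Only one sentence names the FAS. A reader might infer that the general rule in 4.5.1 and Protocol 8.3.8 also direct FAS exclusions. They name no set, exclusion from the PPS alone satisfies the 4.5.1 rule, and 8.3.8 defers to a separate specification that is not among the documents.
- A reader might see a contradiction between Protocol 3.3.1 and SAP 4.4 on unblinding. Section 3.3.1 is a general permission. SAP 4.4 and 4.5 settle it: unblinded subjects stay in the FAS and leave the PPS.
- The power illustration is close to a worst case for 1a. Enrolment is sized on 1b: 3,446 evaluable subjects at a mean 1a attack rate of (8% + 4.8%)/2 = 6.4% give about 220 expected 1a cases, and 10% fewer leaves about 198, still above 191. SAP 6.8 does allow a final analysis once 191 is reached, so the lower figures are possible but not expected under the plan's own assumptions.

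**Conclusion.** The point holds as a conflict within the text. The closing sentence of SAP 4.5.1 disagrees with both FAS Efficacy definitions, with the intent-to-treat label of the primary analysis and with its own section heading. It leaves room for undefined post-randomisation exclusions from the primary set, made before unblinding. The size and direction of any effect are unknown, because the documents give neither a list of FAS-excluding deviations nor an expected number. The power loss is modest even under the assumed shares. The more relevant risk is a result near the boundary.

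Two stronger conclusions are not supported. One is that the primary set becomes a second per-protocol set: where the SAP deals with a specific deviation it keeps the subject in the FAS, and late doses and non-study influenza vaccine are tied to the PPS. The other is that analysis as randomised is breached: that principle decides the arm in which a subject is counted, and 4.5.1 leaves it alone. Only membership of the set is at issue, and that set is already a modified intent-to-treat set because of the day-14 evaluation requirement.

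**What to change.** In SAP 4.5.1:

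- Replace the closing sentence with one stating that the deviation list determines exclusion from the PPS sets only. Add that a subject leaves a FAS only when the section 4.4 criteria for that set are not met, and never for a deviation or unblinding as such.
- Reword the general rule on major deviations so that its unnamed analysis set cannot be read as FAS Efficacy.

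Protocol 3.3.1 and 8.3.8 may be aligned for clarity, but they do not contradict the FAS definition and need not delay the change. The cost is a SAP wording revision before unblinding. The 191 and 104 case targets, the planned enrolment of 3,830 and the stated power are unaffected.

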4.6 Special Subpopulations

Not Applicable.

5 DATA Handling

5.1 Time points and Visit Windows

Assessments required at each study visit is described in Schedule of Assessments ([Appendix A](#))

Day 1 is defined as the day of first dose of the vaccination.

Relative days after Day 1 are calculated as (assessment date – Day 1 date) + 1. Relative days prior to Day 1 are calculated as (assessment date – Day 1 date). The day prior to Day 1 is Day -1

All data will be analyzed using nominal study visits as defined in the Study Schedule see ([Appendix A](#)) and electronic case report form (eCRF).

Throughout the study, unscheduled visits are planned for subjects who manifest influenza-like illness (ILI) symptoms during the influenza season. The data collected at those visits will not be reallocated to one of the clinic visits, but rather the actual date will be listed.

(Protocol Table 1.3).

The following visit windows will be used.

Statistical Analysis Plan – Final v2.0

Sponsor Name: Seqirus UK Limited

Sponsor Protocol ID: V130_14

Table 2: Visit windows for subjects without or unknown previous influenza vaccination history (two dose regimen)

Study part	Scheduled visit	Time interval (days)
Treatment period	Clinic Visit V1	Day 1
	Diary Reminder Call	V1 + 2 Days (-1/+1 Day)
	Clinic Visit V2	V1 + 28 Days (+7 Days)
	Diary Reminder Call	V2 + 2 Days (-1/+1 Day)
	Clinic Visit V3	V2 + 28 Days (+7 Days)
Follow-up Period	Safety Follow-up Call V4	V2 + 90 Days (+7 Days)
	Clinic Visit V5	End of influenza season or V2 + 180 Days (+14 Days) (whichever is longer)
	Clinic Visit V6	V5 + 28 Days (+7 Days)

Table 3: Visit windows for subjects with a previous influenza vaccination history (one dose regimen)

Study part	Scheduled visit	Time interval (days)
Treatment period	Clinic Visit V1	Day 1
	Diary Reminder Call	V1 + 2 Days (-1/+1 Day)
	Clinic Visit V2	V1 + 28 Days (+7 Days)
Follow-up Period	Safety Follow-up Call V3	V1 + 90 Days (+7 Days)
	Clinic Visit V4	End of influenza season or V1 + 180 Days (+14 Days) (whichever is longer)

Visit window deviations will be reviewed prior to unblinding.

5.2 Missing Values – Missing Visits.

Missing, unused and spurious data will be dealt with as such. There is no intention to implement any procedure for replacing missing data.

Titer values recorded as <1:10 will be summarized as 1:5.

No imputation of missing solicited or unsolicited AEs will be used. The percentage of subjects with missing solicited AE assessments (e.g. missing Patient Diary) and

Statistical Analysis Plan – Final v2.0

Sponsor Name: Seqirus UK Limited
Sponsor Protocol ID: V130_14

missing Safety Phone Calls or Safety Assessments will be reported for each time period.

Missing immunogenicity values are considered missing completely at random (MCAR) and therefore will not contain information that impact the result of the analysis (i.e., not informative). Therefore, the key secondary analysis will comprise a complete case analysis only, without introducing any bias. Imputation methods will not be used.

Exclusions of Individual Values for Safety Analyses

Some local and systemic AEs will be directly measured by the subject and will not be subject to a reconciliation process, even if they are biologically implausible. Therefore, these implausible measurements will be removed from the analysis but included in listings.

Implausible measurements are summarized in the table below:

Table 4: Implausible Solicited Adverse Events

Parameter	Implausible measurements
Body temperature	$\leq 33^{\circ}\text{C}$ or $\geq 42^{\circ}\text{C}$
Erythema Measurements	≥ 450 mm or < 0 mm
Induration Measurements	≥ 250 mm or < 0 mm
Ecchymosis Measurements	≥ 250 mm or < 0 mm

6 Statistical Methods

6.1 General Principles

All data processing, summarization and analyses will be performed using [REDACTED] SAS Environment / Version 9.3 (or later) of the SAS® statistical software package.

The FAS will be used for summaries of baseline characteristics and background data; the Safety population will be used for all safety analyses; the analysis population for primary and secondary vaccine efficacy analyses will be based on the FAS Efficacy and repeated on the PPS Efficacy.

In general, summary descriptive statistics of continuous data will be presented as number of observations (n), mean, standard deviation (SD), median, minimum (min) and maximum (max). For categorical variables, statistical summaries will include counts and percentages relative to the appropriate population.

Two-sided 95% (or 97.5%) confidence intervals (CI) will be provided for descriptive statistics, as warranted. The 95% or 97.5% CI for percentages will be exact CIs based upon the binomial distribution. Geometric means and 95% CIs will be calculated by

Statistical Analysis Plan – Final v2.0

Sponsor Name: Seqirus UK Limited
Sponsor Protocol ID: V130_14

taking the anti-logs of the means and 95% CI of the log transformed immunogenicity parameters.

Statistics will be displayed for the following:

- QIVc
- Comparator
- Overall

Summaries by age strata will be:

- 6 through 23 months
- 24 through 47 months

In the summary tables, the strains will be displayed as follows:

- A/H1N1
- A/H3N2
- B/Yamagata
- B/Victoria

All data will be listed.

6.2 Subject Disposition and Data Sets Analyzed

The number of subjects enrolled into the study, in each study population, who completed the study, and the reasons for any premature discontinuation from the study will be presented in summary tables by treatment group, by age strata (6 through 23 months, 24 through 47 months) and overall. The number in the enrolled set will be used as the denominator.

The number of subjects who are excluded from each of the FAS and Per-Protocol populations will be summarized by treatment group, by age strata (6 through 23 months, 24 through 47 months) and overall.

The primary reason for discontinuing the study product, or withdrawing a subject from the study, will be summarized by treatment group, by age strata and overall.

6.3 Protocol Deviations

Major protocol deviations will be tabulated by vaccine group on the All Enrolled Set and will also be listed for subjects who have been entered into the study and assigned a subject number.

6.4 Demographics and Other Baseline Characteristics

All baseline and demographic characteristics will be summarized by vaccine group, age strata, and overall on the Enrolled, Exposed, FAS (Efficacy, Immunogenicity),

Statistical Analysis Plan – Final v2.0

Sponsor Name: Seqirus UK Limited
Sponsor Protocol ID: V130_14

PPS (Efficacy, Immunogenicity) and Safety Sets. This will include age (months), gender, race, ethnicity, weight, height, BMI, medical history, season, country and previous vaccination status.

Derived variables:

Body Mass Index will be calculated according the following formula:

Body Mass Index (kg/m²): Mass (kg) / Height² (m²)

